4.1 ETHICAL ASPECTS

The study will be conducted in accordance with the Guidelines and Regulatory Standards of the National Health Council (Resolution No. 466/12), which establishes the ethical guidelines for research involving human subjects in Brazil.

The benefit of participating in the research is indirect, as the patient contributes to the discovery of scientific evidence that will serve as the foundation for safer and more effective treatment.

Patient personal data, collected through direct contact with the participant during the study, will not be disclosed, and confidentiality will be ensured for all participants. This data will be stored in a Google Drive spreadsheet linked to the researchers institutional email address.

Surgical procedures and the participant's participation in the project may present certain surgical and confidentiality risks inherent to participation, which are outlined in the Informed Consent Form (APPENDIX A).

4.2 TYPE OF STUDY

The study is a randomized, controlled, split-mouth clinical trial.

4.3 LOCATION

The surgeries will be performed at the Outpatient Surgery Center and Surgical

Block of the Hospital de Clínicas de Porto Alegre, located at the address: [name].

4.4 SAMPLE

The sample selection will consist of patients referred to the Oral and Maxillofacial Surgery Unit at the Hospital de Clínicas de Porto Alegre. The selected patients require bilateral extraction of lower third molars under general anesthesia, either due to the complexity of the surgery or due to systemic conditions that contraindicate local anesthesia. Patients who meet these criteria will follow the routine care protocol adopted by the team. During outpatient consultations, laboratory tests (including blood count, PT, aPTT, glucose, AST, ALT, and creatinine), imaging (CT scan of the skull and facial bones), and pre-anesthetic evaluation will be requested. If the tests are normal and cleared by the Anesthesiology team, patients will be placed on the waiting list and contacted when surgery is available. There will be no change to the routine care for patients volunteering in the study. The surgical procedures will be performed by the research team responsible for this study. The inclusion criteria will include patients aged 18 to 60, classified as ASA I or ASA II, who have impacted or semi-impacted lower third molars with similar positioning on both sides, according to the Pell and Gregory classification.³⁸

Patients who can undergo surgery under local anesthesia or who require additional procedures in the same surgical session, will be excluded from the sample. All patients, whether participating in the study or not, will have the right to withdraw from the study at any time without penalty.

Postoperative consultations will be conducted for follow-up, suture removal, and the evaluation and treatment of any potential postoperative complications.

Regarding general anesthesia, since this is a split-mouth study, both patients undergoing total intravenous anesthesia and general inhalational anesthesia will be included. Patients requiring additional intraoperative medications, which may interfere with the data, will be excluded. An example of this is patients receiving tranexamic acid during the procedure, as it could distort bleeding measurements between surgical sites.

The selection of the control group and experimental groups will be determined by a simple randomization in the immediate preoperative period. One surgical site will receive 0.5% bupivacaine + 0.2mL of epinephrine (GA) while the other site will receive 0.75% ropivacaine + 0.2mL epinephrine (GB).

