4.5 PREOPERATIVE CONDUCTS

Each patient selected for the study will be required to complete an Informed Consent Form (APPENDIX A) prior to the clinical procedures. If any participant disagrees with the terms outlined in the form, they will not be included in the study.

The patient's medical history will be taken during an outpatient appointment automatically scheduled via the GERCON system. During this appointment, the team will investigate the patient's current medical condition, other comorbidities, medication use, and known allergies. In addition to the physical examination, imaging tests (panoramic X-rays and/or CT scans) and laboratory tests will be requested. This consultation will also collect sociodemographic data from the sample, assess their health status, and identify any factors that may contraindicate their participation in the study. After the imaging and laboratory tests are completed at the Hospital de Clínicas de Porto Alegre, patients will be placed on the waiting list for surgery. Following the surgical procedure, patients will receive a postoperative care and instructions form (APPENDIX B), standardized medications, and medical notes, if necessary. The VAS (APPENDIX C) and instructions on how to use it will also be provided after the surgery.

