4.7 ASSESSMENT OF VITAL SIGNS DURING THE OPERATIVE PERIOD

Intraoperative vital signs will be assessed by the Anesthesiology and Perioperative Medicine Service of the Hospital de Clínicas de Porto Alegre, always led by the same care team. Heart rate, blood pressure, and oxygen saturation will be measured and recorded before, immediately after, 1 minute after, and 5 minutes after the injection of each anesthetic. Significant changes, such as hypo or hypertension, bradycardia or tachycardia, and hypoxia, will be recorded and presented in the results.

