4.9 EVALUATION OF POSTOPERATIVE ANALGESIA

To assess postoperative analgesia, a VAS will be used, in which patients will rate their pain from zero (no pain) to ten (worst pain ever felt) at different postoperative time points: T0 (immediate postoperative period, as soon as the patient is lucid), T1 (1 hour after T0), T2 (12 hours after T0), T3 (18 hours after T0), and T4 (24 hours after T0). Two scales will be used for each postoperative time point: one for the left side and one for the right side. These values will be recorded, compared, and presented in the results.

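### Section 4.4 excludes patients for interfering intraoperative drugs without limiting the rule to needs known before randomisation; applied as worded, it can drop randomised, injected patients on open-ended and possibly outcome-related grounds.

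*Protocol*

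**What the plan says.** Protocol section 4.4 sets the rule: "Patients requiring additional intraoperative medications, which may interfere with the data, will be excluded". It then illustrates it: "An example of this is patients receiving tranexamic acid during the procedure, as it could distort bleeding measurements between surgical sites". The next paragraph of the same section says that the allocation of sites "will be determined by a simple randomization in the immediate preoperative period". Under section 4.6 a site is infiltrated and surgery starts only afterwards. Section 4.4 also says: "There will be no change to the routine care for patients volunteering in the study".

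Two passages point toward a pre-entry meaning. Section 4.4 has a similarly worded rule for patients "who require additional procedures in the same surgical session, will be excluded from the sample", and the outpatient visit in section 4.5 is meant to "identify any factors that may contraindicate their participation in the study".

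Three kinds of outcome are collected on each patient. Bleeding is measured per site (4.8). Vital signs "will be measured and recorded before, immediately after, 1 minute after, and 5 minutes after the injection of each anesthetic" (4.7). Pain is scored at T0 to T4, and "Two scales will be used for each postoperative time point: one for the left side and one for the right side" (4.9). Section 4.10 plans a descriptive account of vital signs and a comparison of averages for pain and bleeding. Section 5 has surgeries continue until the planned number is reached, without saying whether excluded patients are replaced.

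**The concern.** A rule that can act once surgery is under way acts after sites have been randomised and usually after at least one study drug has been injected. Three features make that awkward here.

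- **It is open-ended.** Any drug that might affect the data qualifies. There is no list of drugs and no named decision-maker. Section 6.2 has the research team do both the surgery and the analysis.
- **It may depend on an outcome.** A haemostatic drug may be given because a site bleeds heavily, and bleeding is compared between the anaesthetics. A drug given for a change in blood pressure or heart rate could also fall under the wording, and section 4.7 promises to report such changes. The protocol does not say that such drugs are used or what prompts them, but nothing in the rule keeps these cases out.
- **It removes the patient, not the affected measurement.** In the tranexamic acid example the stated worry is bleeding, yet the pain scores and vital signs go as well.

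At stake are a possible bias in the bleeding comparison, avoidable loss of pain and vital-sign data in a very small trial, and possible loss of the haemodynamic events that bear on the trial's toxicity rationale.

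**Working it through.** **1. Timing.** Randomisation is immediately preoperative (4.4), then a site is infiltrated, then surgery begins (4.6). A drug first needed during surgery therefore comes after randomisation and normally after at least one injection. Nothing in 4.4 limits the rule to needs foreseen earlier.

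**2. Cost of one exclusion, from the documents.** The plan has 15 patients and 15 × 2 = 30 sites. It gives no expected number of exclusions.
- Pairs: 1/15 = 6.7%, if the patient is not replaced.
- VAS scores: 5 times × 2 sides = 10.
- Vital-sign sets: 4 times × 2 injections = 8.

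The last two assume that data already collected are dropped with the patient, which the text implies but does not spell out.

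**3. Bias in bleeding, illustration only.** The documents give no bleeding SD, between-site correlation, trigger or frequency, so all of these are assumed. Site bleeding is taken as bivariate normal with means +δ/2 and −δ/2 about the overall mean, correlation 0.5 and order 50:50. A patient is excluded when bleeding exceeds a cut-off c above the overall mean. For the either-site trigger the retained difference is E[A − B | A < c, B < c]. It was simulated with 4,000,000 patients per scenario.

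| Assumed site SDs, trigger | True δ | c = 2 | c = 1.5 | c = 1.0 |
|---|---|---|---|---|
| Both 1.0, either site | 0.50 | 0.470 | 0.439 | 0.396 |
| Both 1.0, first site only | 0.50 | 0.487 | 0.475 | 0.465 |
| Both 1.0, either site | 0 | 0.00 | 0.00 | 0.00 |
| Heavier arm 1.0, other 1.3, either site | 0.50 | 0.54 | 0.55 | 0.57 |
| Heavier arm 1.3, other 1.0, either site | 0.50 | 0.37 | 0.29 | 0.20 |
| 1.0 and 1.3, either site | 0 | 0.08 | 0.13 | 0.18 |

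With equal SDs, attenuation is 1 − 0.470/0.50 = 6%, then 12% and 21%, for the either-site trigger, and 3%, 5% and 7% for the first-site trigger. Over correlations of 0.3 to 0.7 the either-site figures run 4–8%, 8–17% and 14–27%. With unequal SDs the shift can go either way, and a true zero no longer stays at zero. In that last row the apparent excess falls on the arm with the smaller SD.

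**4. Against sampling error with 15 pairs.**
- Equal SDs: SE = √[2(1 − 0.5)]/√15 = 0.26. The largest shift in the table is 0.50 − 0.396 = 0.10.
- SDs 1.0 and 1.3: SE = √(1 + 1.69 − 1.3)/√15 = √1.39/√15 = 0.30. The largest shift is 0.50 − 0.20 = 0.30, about one standard error.

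**5. Does keeping everyone remove the problem?** Not for bleeding. Take equal SDs, a true difference of 0.50 and an assumed drug effect of 1.0 SD. The all-patient estimate is 0.514 / 0.533 / 0.561 if a first-site trigger lowers only the second site. It is 0.473 / 0.435 / 0.379 if the drug acts only at the site where it is given. At c = 1.0 these compare with 0.465 and 0.396 under exclusion with the corresponding trigger. Neither approach is always less biased.

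**The case against.** The strongest reply is that this is an eligibility rule. It stands in the sample section before the randomisation paragraph, it is phrased like the rule on additional procedures, and patients are screened by laboratory tests, anaesthetic clearance and medical history. A drug given during surgery can be planned in advance, so the example fixes when the drug is given, not when the patient is excluded. This reading is possible and it stands. A reader might infer that the protocol definitely prescribes post-randomisation exclusion, and the text does not go that far. It leaves both meanings open.

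A second reply is that the ground is not bleeding alone. That is right: the general clause refers to the data as a whole, and bleeding is only the example. The mismatch between reason and scope holds for haemostatic drugs, not for every drug the rule might cover.

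Third, both sites of a patient leave together, so the arms stay balanced, and the harm depends on events whose frequency is unknown. Both statements are correct. Balance does not remove selection on the outcome, as the table shows.

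Fourth, analysis sets and sensitivity analyses often belong in an SAP, which is not at hand. But the exclusion rule is stated in the protocol itself, so its wording can be judged there.

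**Conclusion.** The concern holds in limited form. The wording of section 4.4 admits exclusion of randomised and injected patients on an open-ended ground that may be related to outcomes, and it removes more data than the example justifies. The firm figures are 1 of 15 pairs (6.7%), 10 VAS scores and 8 vital-sign sets per exclusion. The first applies only without replacement; with replacement the number is kept but the selection remains.

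The size of any bleeding bias cannot be derived from the documents. A reader might infer that it always pulls toward zero, vanishes when the anaesthetics do not differ, or is bound to be small. Those statements need equal bleeding spread at the two sites, which the documents do not establish. Under the assumed SDs of 1.0 and 1.3 the shift goes either way and reaches about one standard error. The case for change rests on the unclear timing and the avoidable loss of data, not on a particular amount of bias.

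**What to change.** Reword section 4.4 so that the exclusion applies only to needs known before randomisation. For drugs first given after randomisation:

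- keep the patient in the study, with all VAS scores, vital-sign readings and events;
- record the drug, its time, the reason and the site in progress;
- report the bleeding comparison with all randomised patients and again without those given a haemostatic drug, stating how many were affected.

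This changes data handling only, not who receives which drug. The cost is a wording change, one case-report line and one sensitivity analysis, with no extra patients or procedures. The downside is that a haemostatic drug can itself distort the all-patient bleeding estimate in either direction, so neither result is definitive alone and both should be shown.

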4.5 PREOPERATIVE CONDUCTS

Each patient selected for the study will be required to complete an Informed Consent Form (APPENDIX A) prior to the clinical procedures. If any participant disagrees with the terms outlined in the form, they will not be included in the study.

The patient's medical history will be taken during an outpatient appointment automatically scheduled via the GERCON system. During this appointment, the team will investigate the patient's current medical condition, other comorbidities, medication use, and known allergies. In addition to the physical examination, imaging tests (panoramic X-rays and/or CT scans) and laboratory tests will be requested. This consultation will also collect sociodemographic data from the sample, assess their health status, and identify any factors that may contraindicate their participation in the study. After the imaging and laboratory tests are completed at the Hospital de Clínicas de Porto Alegre, patients will be placed on the waiting list for surgery. Following the surgical procedure, patients will receive a postoperative care and instructions form (APPENDIX B), standardized medications, and medical notes, if necessary. The VAS (APPENDIX C) and instructions on how to use it will also be provided after the surgery.

4.6 SURGICAL TECHNIQUE

The procedure will be performed in a hospital setting, where patients undergo a single surgery for the extraction of the lower right and lower left third molars. Throughout the perioperative period, patients will be closely monitored, with their vital signs observed by both the surgical team and anesthesiology teams. As prophylaxis, patients will receive 900mg of clindamycin intravenously at the start of the procedure. The patient will be positioned supine on a hospital stretcher and placed under general anesthesia. Extra and intraoral antisepsis will be performed using a 0.12% chlorhexidine digluconate aqueous solution, and sterile surgical drapes will be used. Following these initial steps, one of the surgical sites (as selected) will be infiltrated with either 6 mL of 0.5% racemic bupivacaine + 0.2 mL of epinephrine or 4 mL of 0.75% ropivacaine with 0.2 mL of epinephrine, with approximately 25 mg of anesthetic injected. The surgical procedure will then begin. A Neumann incision with diverticulum will be made on the distal side of the adjacent mandibular second molar, followed by mucoperiosteal detachment, osteotomy, and odontosection (if necessary). The tooth will then be luxated and extracted using levers. The surgical wound will be cleaned and sutured with single or X-shaped stitches using 4-0 polyglactin sutures. Suture removal will take place between 7 and 10 days postoperatively. Before discharge, while

still in the hospital, patients will receive intravenous administration of 2g of dipyrone every 6 hours, 40mg of tenoxicam once daily, 100mg of tramadol every 8 hours, 600mg of clindamycin every 6 hours, and 4mg of ondansetron every 8 hours.

Postoperative instructions and necessary medications will be provided to patients both verbally and in writing, according to the protocol recommended by the hospital (APPENDIX B). Suture removal will be performed in an outpatient setting at the Hospital de Clínicas de Porto Alegre between 7 and 10 days postoperatively.

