The removal of third molars is one of the most frequently performed procedures in dentistry, and can be carried out in a hospital setting under general anesthesia. In such cases, local anesthetics are often administered at the surgical site in addition to general anesthesia, to promote better hemostasis and postoperative analgesia. Bupivacaine is a local anesthetic commonly used in these situations. However, its known cardiotoxic and neurotoxic effects, as reported in the literature, have led to increased interest in safer alternatives, such as ropivacaine. **Objective:** to evaluate whether there is a significant difference between bupivacaine and ropivacaine in terms of postoperative analgesic efficacy, intraoperative hemostasis, and patient vital signs during the intraoperative period. **Materials and Methods:** This was a randomized, controlled, split-mouth clinical trial. The sample size was based on a similar previously published study and included 15 participants ($n = 30$). As this study also follows a split-mouth design, each of the 15 patients underwent two tooth extractions. All patients had indications for the removal of both lower third molars under general anesthesia. Surgical extractions were performed in a single session, with bupivacaine (Group A) administered at one surgical site and ropivacaine (Group B) at the other. The procedures were carried out at the Hospital de Clínicas de Porto Alegre. Vital signs were continuously monitored by the same anesthesiology team, with data collected at the time of drug injection (before and immediately after), as well as one minute and five minutes post-injection. Intraoperative bleeding was measured by calculating the volume of blood aspirated into the collection vial, from the time of incision to the final suture, at each surgical site. To minimize systemic interference from the anesthetic agents, their administration was alternated between patients. Postoperative analgesia was self-reported by the patients using a Visual Analog Scale (VAS) for each side at various postoperative time points. A descriptive analysis will be conducted on the clinical data obtained through these measurements.

Key-words: Third Molar; Anesthetics, Local; Surgery, Oral

SUMÁRIO

SUMMARY	5
1 INTRODUCTION	6
2 LITERATURE REVIEW	8
3 OBJECTIVES	10
4 METHODOLOGY	11
4.1 ETHINCAL ASPECTS	11
4.2 TYPE OF STUDY	11
4.3 LOCATION	12
4.4 SAMPLE	12
4.5 PREOPERATIVE CONDUCTS	13
4.6 SURGICAL TECHNIQUE	13

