2 LITERATURE REVIEW

2.1 RACEMIC BUPIVACAINE

Bupivacaine is a potent local anesthetic from the amide group, widely used in regional anesthesia, epidural anesthesia, spinal anesthesia, and local anesthesia. It is available in three different concentrations: 0.25%, 0.5%, and 0.75%.²¹ It is called racemic because it is an equimolar mixture of dextrorotatory and levorotatory isomers.²² Bupivacaine has a slow onset of action (6 to 10 minutes), a half-life of 2.7 hours, and intrinsic vasodilatory potential. It is commonly used in more extensive procedures that require prolonged intraoperative and postoperative anesthesia.¹¹ To reduce intraoperative bleeding, toxicity, and the required dose for anesthesia, vasoconstrictors are frequently added to bupivacaine, with epinephrine being one of the most commonly used substances.²³

Bupivacaine was first synthesized in 1957 and introduced to the market in the mid-1960s. As its use increased, so did reports of adverse effects, including toxicity to the central nervous system and cardiovascular system.²⁴ Bupivacaine is closely associated with seizures, severe bradycardia, and cardiac arrest, which are often

resistant to conventional cardiopulmonary resuscitation techniques.²⁵ These side effects are frequently linked with overdose or accidental intravascular injection.²⁶

Duo to these concerns, several studies have been conducted to better understand the cause of bupivacaine's toxicity, ultimately leading to the exploration of isomers and the development of new anesthetic agents.²⁷

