4 MATERIALS AND METHODS

The study is designed as a randomized, controlled, split-mouth clinical trial. Patients receiving 0.5% bupivacaine with 0.2 mL of epinephrine are defined as group A (GA), while patients receiving 0.75% ropivacaine with 0.2 mL of epinephrine are classified as group B (GB).

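### Protocol section 4.6 gives two study-drug doses in one sentence: the stated volumes and strengths give 30 mg per site, but the stated mass is about 25 mg

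*Protocol*

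**What the plan says.** Section 4.6 (Surgical Technique) specifies the infiltration of a site as "6 mL of 0.5% racemic bupivacaine + 0.2 mL of epinephrine or 4 mL of 0.75% ropivacaine with 0.2 mL of epinephrine". The sentence then closes with a mass that covers both options: "with approximately 25 mg of anesthetic injected".

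The strengths, 0.5% for bupivacaine and 0.75% for ropivacaine, are repeated in sections 3.1 and 3.2 (objectives), at the start of section 4 (group definitions) and in section 4.4 (allocation of sites). None of those places gives a volume or a mass of anesthetic, so section 4.6 alone fixes how much of each drug is given.

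**The concern.** Volume, strength and mass are tied by a single product, so any two of them determine the third. Here all three are stated and they do not agree. A team working from the mL figures and a team working from the mg figure would inject different amounts of the two drugs that the trial compares.

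What is at stake is the definition of the intervention and its reporting. A paper that copied this sentence would publish two doses, and a reader could not tell which one produced the pain, bleeding and vital-sign results.

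**Working it through.** **Inputs, all from section 4.6**

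- Group A: "6 mL of 0.5% racemic bupivacaine + 0.2 mL of epinephrine"
- Group B: "4 mL of 0.75% ropivacaine with 0.2 mL of epinephrine"
- Stated mass: 25 mg, qualified as approximate. I read it as per site, the reading closest to the volumes. Read per patient it would be further off, because the two sites together give 60 mg.

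**Formula**

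Mass (mg) = volume (mL) × strength (%) × 10, because 1% weight per volume is 10 mg/mL. So 0.5% is 5 mg/mL and 0.75% is 7.5 mg/mL.

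**Attempt to reproduce the stated 25 mg**

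The text does not say whether the 0.2 mL of epinephrine is added to the stated volume or lies within it, so three readings were tried.

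| Reading | Bupivacaine | Ropivacaine | Both sites |
|---|---|---|---|
| Epinephrine added, everything injected | 6 × 5 = 30 mg | 4 × 7.5 = 30 mg | 60 mg |
| Epinephrine inside the stated volume | 5.8 × 5 = 29.0 mg | 3.8 × 7.5 = 28.5 mg | 57.5 mg |
| Epinephrine added, only 6 or 4 mL of the mixture injected | 30 × 6/6.2 = 29.03 mg | 30 × 4/4.2 = 28.57 mg | 57.6 mg |
| Stated mass | 25 mg | 25 mg | 50 mg |

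None of the three gives 25 mg.

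**Size of the gap**

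- Largest: 30 − 25 = 5 mg, and 5/25 = 20%.
- Smallest: 28.5 − 25 = 3.5 mg, and 3.5/25 = 14%.

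**Does the word for approximation cover it?** The protocol sets no tolerance. As a generous yardstick of my own, a figure rounded to the nearest 5 mg and reported as 25 would lie between 22.5 and 27.5 mg. The lowest reading, 28.5 mg, is outside that band.

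**Working back from 25 mg**

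- Strength needed at the stated volumes: 25/6 = 4.17 mg/mL = 0.417%, and 25/4 = 6.25 mg/mL = 0.625%. Neither strength appears in the protocol. For bupivacaine, section 2.1 lists 0.25%, 0.5% and 0.75%, which at 6 mL give 15, 30 and 45 mg. The protocol has no such list for ropivacaine.
- Volume needed at the stated strengths: 25/5 = 5.0 mL instead of 6 mL, and 25/7.5 = 3.33 mL instead of 4 mL.

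**Balance between the two sides**

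Under each reading the sides differ by 30 − 30 = 0 mg, 29.0 − 28.5 = 0.5 mg, or 29.03 − 28.57 = 0.46 mg.

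**The case against.** The strongest objection is about weight. The outcomes are pain scores, aspirated blood volume and vital signs. The analysis in section 4.10 compares averages and describes changes, and no step takes the mg figure as an input. The protocol does give a product, strength and volume for each group, so one could call this a single conflicting figure and not a missing dose. It is true that no estimate is distorted, and that is accepted here. But the conflict sits in the only sentence that says how much of each study drug is given, and the documents do not show which figure is the faulty one. That is more than a clerical matter.

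Two further readings could bring the mass down to 25 mg:

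- **Part of the volume is delivered.** 25 mg is 5/6 of the stated volume in both groups. But the text says that the site is infiltrated with the full 6 or 4 mL, and nothing mentions a residue or discarded volume.
- **The mg figure means base and not salt.** The introduction names both drugs as hydrochlorides. A base fraction of 25/30 = 0.833 would close the gap. The documents give no fraction. If it were assumed to lie between 0.83 and 0.92, 30 mg of salt would be 24.9 to 27.6 mg of base. Nothing in the protocol says that mass is expressed as base.

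These two readings limit the claim: it is the epinephrine-volume readings that fail to give 25 mg, not every conceivable one. Neither rescues the sentence as written. If either was meant, the sentence would still have to say so.

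Where the epinephrine sits moves the mass by at most 1.5 mg, so it is secondary to the conflict between 25 and 30 mg.

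**Conclusion.** The concern holds. Section 4.6 states a mass of about 25 mg per site, while its own volumes and strengths give 30 mg, or 28.5 to 29.0 mg when the epinephrine volume is allowed for. The gap is 3.5 to 5 mg per site and 7.5 to 10 mg per patient over both sites (57.5 − 50 and 60 − 50).

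This rests on reading percent as weight per volume, the 25 mg as per site, and mass as that of the drug at its labelled strength.

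It is an error of dose specification and reporting, not a source of bias, provided that one rule is applied to both sides. It must be corrected because the dose under comparison is not uniquely defined anywhere in the protocol.

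**What to change.** The investigators should:

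1. Reconcile volume, strength and mass in section 4.6 so that the three agree for each drug. This review takes no position on which figure is right.
2. State whether the 0.2 mL of epinephrine is in addition to the stated volume or part of it, and on what basis the mg figure is expressed.
3. Report the mL and mg actually injected on each side.

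The Summary uses the past tense ("each of the 15 patients underwent two tooth extractions"), while section 4.6 uses the future. If surgery has already been done, the reported figures should come from the operative and anesthesia records and not from the protocol sentence.

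The cost is one sentence in section 4.6 and two reported figures per side. If the mass turns out to be the wrong figure, only text changes. If a volume or strength is wrong, the prepared mixture changes too or, after surgery, the report must state what was given. The documents do not show which case applies.
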